Pre-test/ post-	level 1 (pupil)	0.88 ¹	0.88	0.88	0.88
test	level 2 (class)	-	-	-	-
correlations	level 3 (school)	0.62	0.62	0.62	0.62
Intracluster	level 2 (class)	-	-	-	-
correlations (ICCs)	level 3 (school)	0.15 ²	0.15	0.15	0.15
Alpha		0.05	0.05	0.05	0.05
Power		0.8	0.8	0.8	0.8
One-sided or two-sided?		Two-sided	Two-sided	Two-sided	Two-sided
Average cluster size		7	3	8	
	intervention	50	50	50	50
Number of schools	control	50	50	49	49
	total	100	100	99	99
	intervention	350	150	406	

¹ Villarreal (2015) undertook a test review of the WJIV standard battery of tests and found correlations in the range of .83-.95. In the Woodcock Johnson IV manual, test-retest correlations were between 0.83-0.95 for the age 7-11 group (p.94). However, these sort of test-re-test reliability analyses tend to be over very short periods (e.g. one day).

² We have selected an ICC of 0.15 as this represents a trade-off in that the schools are centred on a specific small geographical region, but on the other hand recognises that some EEF trials amongst Early Years have been higher at 0.17-0.19.

		Prot	Protocol		nisation
		OVERALL	FSM	OVERALL	FSM
Number of pupils	control	350	150	387	
	total	700	300	793	

With the above parameters, at the protocol stage, we estimated that it is possible to achieve an MDES of 0.195 for the main effect and 0.22 for FSM subgroup analysis. During recruitment we found that the number of children failing their initial vision screening was slightly higher than expected giving an average cluster size of 8 children in the study. Despite recruiting one school less than planned, the MDES remained effectively stationary at 0.194. The FSM estimate at randomisation will be updated once we receive the matched data from the DfE containing the FSM indicator.

Analysis

The analysis will examine the impact of the Glasses in Classes intervention in comparison to the business-as-usual control condition on the basis of intention to treat (ITT) using a two-level multilevel model using Maximum Likelihood estimation.

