As per EEF standards, headline figures will be presented throughout. In addition, as set out in Corcoran (2016, p.69) we will carry out an analysis to examine the overall and differential attrition rates that may bias the estimated impact of the Glasses in Classes treatment condition. However, there is an expectation that overall attrition would be less than 10% and the difference between the treatment and control schools less than 5%. These thresholds being within acceptable standards for WWC guidelines (WWC Standards and Procedures Handbook, Version 4.1). This expectation for low attrition and potential for bias is due to random factors and the primary reason for pupil attrition being independent of the treatment, such as families moving. However, attrition at the pupil level will be monitored and the structure of the missing data will be assessed using the MCAR test (Little, 1988). If the structure of the missing data is not missing completely at random (MCAR) or the combination of a non-MCAR test results and pupil overall attrition that is above a 5% threshold, then multiple imputation methods will be considered for a sensitivity analysis (Little and Rubin, 2002).

Compliance

The comparison group variable will be used as the instrumental variable to predict compliance which is a dichotomously measured indicator that distinguishes between the randomly assigned treatment and comparison students. The use of the comparison group is standard per WWC guidelines (WWC Standards Handbook, Version 4.1, p. 46). The variable that will be used as the endogenous independent variable that estimates compliance will be a dichotomous variable that indicates full fidelity vs incomplete fidelity of implementation. The fidelity variable could be derived from two fidelity sub-domains: child attendance with optometrist with prescription glasses and whether the pupil had a full set (two pairs of glasses) compared to a single set or no glasses. These variables could be combined into an index and then dichotomised based on full fidelity. Full fidelity and optimal compliance would consist of those pupils that had greater than 80% attendance (percent of total optometrist sessions attended) with the optometrist and had a full set of prescription glasses. The use of the compliance variable as a dichotomous endogenous independent variable is consistent with WWC guidelines (WWC Standards Handbook, Version 4.1, p. 46). The level at which compliance is measured is at the pupil level.

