
To assess treatment effects in the presence of non-compliance, CACE analysis will be conducted using a Two-stage least squares (2SLS) analysis that utilizes asymptotic standard errors. The first-stage of the analysis will be specified as:

Compliance
$$y_i = \beta_{0i} + \beta_1 Treatment_i + \beta_2 Pretest Outcome_i + \varepsilon_i$$

Where, i is notation for all individuals in the sample, Compliance y is the endogenous independent variable that measures compliance with the treatment measured as a dichotomous variable, Treatment is a dichotomous variable that captures the random assignment of students to treatment or control groups by school, the Pretest outcome is the pretest measure of the outcome variable, and ε is the error term. This first stage equation is

estimated using OLS and predicted values of the compliance variable will be generated from these estimates and denoted as Compliance \hat{y}_i for the final stage of analysis. The predicted compliance indicator will measure the contrast between those intervention pupils with optimal compliance to the intervention and those intervention pupils with minimum compliance to the intervention in addition to control pupils.

The structural equation with the final stage will be specified as:

Posttest Outcome
$$y_i = \beta_{0i} + \beta_1 Compliance \hat{y}_i + \beta_2 Pretest Outcome_i + \varepsilon_i$$

Where, Outcome y is the posttest outcome of interest, Compliance \hat{y} is the predicted values of the endogenous independent variable that measures compliance from the first stage of analysis, Treatment is a dichotomous variable that captures the random assignment of students to treatment or control groups by school, Pretest outcome is the pretest measure of the outcome variable, and ε is the error term.

In terms of measuring compliance properly, if the theoretical thresholds for both the attendance with optometrists and pairs of glasses received do not exceed adequate thresholds of the intervention group sample, this may suggest that the theoretical thresholds for attendance may be too strict. In that instance, a Jenks natural breaks optimisation will be conducted on the attendance fidelity measure using raw percentage of attendance (Jenks 1967). This will be done to determine an adequate classification of attendance and inclusion for the purposes of compliance with the study intervention.

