In sum, this CACE analysis will be used to assess the potential impact of random assignment and other covariates on compliance with the treatment. These estimates in turn will be used along with all covariates to predict the outcome of interest and therefore provide an unbiased estimate of the impact of compliance and non-compliance on the outcome. Hedge's g will be calculated to determine the effect size. Statistically insignificant and non-meaningful effects of the compliance variable will indicate that noncompliance in the study did not have an impact on the outcomes.

Intra-cluster correlations (ICCs)

Intra-cluster correlations (ICCs) will be calculated from a multilevel null model (i.e. one without the treatment or pre-test covariates, but including the school level) for the primary reading achievement outcome. The formula is presented below. As part of the appendices we will also provide ICC calculations for the secondary reading, mathematics and visual acuity outcomes.

$$ICC = \frac{\sigma_{school}^2}{(\sigma_{school}^2 + \sigma_y^2)}$$

Effect size calculation

EEF standard practice will be followed in reporting effect sizes (Hedges *g*). The formula is presented below:

$$ES = \frac{\overline{Y}^t - \overline{Y}^c}{\sqrt{(\sigma_{school}^2}^2 + \sigma_y^2)}$$

Effect size quantities will be computed from the Ime4 using the sim() function in the Applied Regression Modelling package (arm) in R to generate a posterior distribution from which 95% confidence intervals can be calculated.

References

- Bafumi, J. & Gelman, A. (2006) Fitting multilevel models when predictors and group effects correlate. 2006 Annual Meeting of the Midwest Political Science Association, Chicago, II.

 http://www.stat.columbia.edu/~gelman/research/unpublished/Bafumi_Gelman_Midwest06.pdf

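### The SAP reads a non-significant, non-meaningful CACE estimate as showing that noncompliance had no impact, with no threshold, interval or margin to support that conclusion

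*SAP*

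**What the plan says.** The SAP's Compliance section plans a complier average causal effect (CACE): "CACE analysis will be conducted using a Two-stage least squares (2SLS) analysis that utilizes asymptotic standard errors". Randomised arm is the only instrument: "The comparison group variable will be used as the instrumental variable to predict compliance". The one endogenous variable is a pupil-level yes/no indicator of full fidelity: "Full fidelity and optimal compliance would consist of those pupils that had greater than 80% attendance", together with a full set of glasses. The contrast is with "those intervention pupils with minimum compliance to the intervention in addition to control pupils". The pre-test is the only covariate, and neither equation has a school term. The ITT analysis, by contrast, is fitted "using a two-level multilevel model using Maximum Likelihood estimation".

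The closing paragraph says the estimates will "provide an unbiased estimate of the impact of compliance and non-compliance on the outcome", that Hedges' g will be calculated, and then: "Statistically insignificant and non-meaningful effects of the compliance variable will indicate that noncompliance in the study did not have an impact on the outcomes". The rule therefore has two conditions, non-significance and a negligible size. Neither the Compliance section nor any other part of the SAP says what size counts as negligible.

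**The concern.** The rule fixes in advance a substantive conclusion from a null finding. A non-significant estimate with a wide interval is compatible both with no effect in compliers and with an effect large enough for poor uptake to have cost the trial a good deal. Without a margin, the two cannot be told apart, and the size condition could be settled after the results are seen.

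This matters because uptake is the reason for the intervention. The protocol's Intervention Summary cites about 30% of children with a treatable deficit in high-poverty communities who do not attend or do not wear their glasses. If the ITT result is null, readers will ask whether the programme or its uptake failed. The rule could give the wrong answer to that question with the authority of a prespecified analysis.

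**Working it through.** **Reproducing the SAP's precision.** Inputs from SAP Table 2, randomisation stage: ICC 0.15, pre/post correlations 0.88 (pupil) and 0.62 (school), 99 schools (50 and 49), 8 pupils per school, two-sided alpha 0.05, power 0.80.

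Variance of the ITT effect = [0.15 × (1 − 0.62²) + 0.85 × (1 − 0.88²)/8] / (50 × 49/99) = (0.09234 + 0.02397)/24.747 = 0.00470, so SE = 0.0686.

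MDES = (1.985 + 0.845) × 0.0686 = 0.194, which is the SAP's figure.

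**What the CACE is.** With one binary instrument and one endogenous variable, the 2SLS coefficient is the single-level ITT coefficient divided by the arm difference in compliance. In simulated trials of this design (99 schools of 8 pupils, 2,000 per scenario) the two agreed to rounding error. Control pupils are placed with the non-compliers, so noncompliance is taken as one-sided. Writing c for compliance in the intervention arm, ITT = c × CACE, and dilution = CACE − ITT = (1 − c) × CACE.

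**Width of the interval.** With a valid clustered SE, and c treated as known, the 95% half-width of the CACE is 1.96 × 0.0686/c:
- c = 1.0: 0.13 SD
- c = 0.7: 0.19 SD
- c = 0.5: 0.27 SD
- c = 0.3: 0.45 SD

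At c = 0.5 even an estimate of exactly zero has an interval of about −0.27 to 0.27, which contains the 0.2 SD named in the SAP's sample-size section. The interval for dilution at c = 0.5 is half as wide, 0.5 × 0.27 = 0.13 SD either side.

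**How often both conditions are met when noncompliance did matter.** The documents give neither c, nor a complier effect, nor a threshold, so all three are assumed: complier effect 0.194 SD, c from 0.9 down to 0.3, and a threshold T of 0.05, 0.10 or 0.194 SD. The estimated ITT is normal with mean 0.194c and SD 0.0686. The rule fires when its absolute value is below the smaller of 1.96 × 0.0686 = 0.134 and T × c.

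| c | True dilution (SD) | Non-significant | Both, T = 0.05 | Both, T = 0.10 | Both, T = 0.194 |
|---|---|---|---|---|---|
| 0.9 | 0.02 | 28% | 3% | 11% | 28% |
| 0.7 | 0.06 | 49% | 6% | 17% | 49% |
| 0.5 | 0.10 | 71% | 11% | 23% | 50% |
| 0.3 | 0.14 | 86% | 12% | 24% | 46% |

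**With the SE as the SAP writes it.** The 2SLS has no school term. The conditional ICC is 0.09234/(0.09234 + 0.19176) = 0.325, the design effect is 1 + 7 × 0.325 = 3.28, and the SE is too small by √3.28 = 1.81. The significance limit on the ITT scale falls to 0.134/1.81 = 0.074. At c = 0.5 the rule then fires in 11%, 23% or 36% of trials, and at c = 0.3 in 12%, 24% or 46%.

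**The case against.** The best defence is that the rule is not empty. Under one-sided noncompliance, dilution is (1 − c) × CACE, so for c below 1 a complier effect of zero and a dilution of zero are the same hypothesis. If the complier effect really is nil and assignment acts only through compliance, the SAP's conclusion is correct. The rule also demands a small estimate, not just a large p-value. All of this stands. It narrows the fault to concluding no impact from non-rejection without a margin.

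Several stronger readings are tempting, and the documents do not support them:
- **That non-significance alone triggers the conclusion.** It does not; the SAP requires both conditions. For a complier effect of 0.30 SD and 40% compliance, non-significance occurs in 58% of trials (valid SE), but both conditions hold in 5%, 11% or 27% for the three thresholds.
- **That the CACE p-value says nothing about whether noncompliance mattered.** The identity above shows otherwise.
- **That the CACE test merely repeats the planned ITT test.** This is close to true with matching standard errors. As written, the unclustered 2SLS and the multilevel ITT reached the same verdict in only 65% to 88% of simulated trials.
- **That the rule misleads ever more often as compliance falls.** This is true of the significance condition. Under the full rule the rate is roughly flat between 50% and 30% compliance.
- **That a significant CACE would be read as showing an impact.** The SAP states no such converse.

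It is also fair to say that this is one interpretive sentence in a supplementary analysis, which touches neither the sample nor the primary model.

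**Conclusion.** The rule is invalid as written: followed exactly, it can report that noncompliance had no impact when it removed half of a real effect. In the illustration that happens in about 11% to 50% of trials with a valid SE, or 11% to 36% with the unclustered SE, depending on a threshold the SAP leaves open. These rates rest on an assumed complier effect of 0.194 SD, 50% compliance, one-sided noncompliance, and assignment acting only through compliance. The interval widths rest only on the SAP's sample-size inputs and the assumed compliance.

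The claim of unbiasedness is also too strong. 2SLS is consistent under conditions that the Compliance section does not state. One of them, the exclusion restriction, is open to doubt here, because an intervention pupil with a single pair of glasses counts as not compliant and may still benefit.

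This is a moderate correction to a secondary conclusion. The primary ITT result does not depend on it.

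**What to change.** - Delete the sentence.
- Report compliance by arm, and the CACE with a school-clustered 95% interval beside the ITT estimate.
- Describe dilution as the difference between CACE and ITT, with its interval.
- Conclude that noncompliance had little impact only if the CACE interval lies wholly within a margin set before the outcome data are seen. Say in advance that the answer may be inconclusive: at 50% compliance a margin of 0.2 SD could not be met even by an estimate of zero.
- Replace the claim of an unbiased estimate with one that is consistent under the exclusion restriction and monotonicity.
- Do not add a statement that the CACE p-value carries no information on noncompliance; that would be wrong.

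The cost is a few sentences in the Compliance section and a cluster-robust option in the 2SLS. No new data are needed.
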